The Evaluation Of The Efficiency Of Micro- osteoperforation

Date :April 28, 2016

STUDY PROTOCOL

The aim of this study was to evaluate the effectiveness of micro-osteoperforations (MOP) performed in the alignment stage.

This was a 2-arm parallel-group, randomized, controlled trial with a 1:1 allocation ratio

The protocol of the study was approved by Izmir Katip Çelebi University Clinical Research Ethics Committee dated 18.05.2016 (no: 94) and T.C. Ministry of Health, Turkey Pharmaceuticals and Medical Devices Agency dated 09.09.2016 (document number: 228 418) was approved by decision.

Based on Mehr's (1) study, the dependent sample t-test using the G * Power 3.1 software program (Franz Faul, Universität Kiel, Germany) showed that 24 patients had an effect width of $d = 1.05$ and $\alpha = 0.05$ significance level. it was determined that the number of samples formed 80% power. Assuming a 15% exclusion rate, a total of 28 patients (14 patients) were included in the study.

The patients who applied to the Department of Orthodontics of the Faculty of Dentistry of Izmir Katip Çelebi University and who were found to comply with the study criteria were informed verbally and in writing. Written informed consent was obtained from patients and parents who agreed to participate in the study. A total of 28 patients (12 males and 16 females) aged between 12 and 27 years, with a diameter of more than 5 mm in terms of the Little irregularity index, were included in the study. The study groups were composed of 14 patients (4 boys, 10 girls) in the MOP applied (MOP+) group and 14 patients (8 boys, 6 girls) in the MOP not applied (MOP-) group.

The following inclusion and exclusion criteria were considered in the selection of patients to be treated: Inclusion Criteria:

- All permanent teeth have been removed (except the 3rd molars)
- Presence of more than 5 mm crowding in the lower arc according to Little irregularity index (1)

- Gingival and periodontal indices less than 1
- Good oral hygiene
- Patient and / or guardian volunteering to participate in the study
- Exclusion Criteria:
 - Congenital missing or pulled teeth
 - Severe skeletal malocclusion
 - Systemic disease
 - Presence of periodontal disease
 - Radiographic determination of bone loss

- Gingival pocket depth of more than 4 mm • Previous orthodontic treatment

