Table 1 presents the gender, age distribution and baseline Little irregularity index data of the patients. Table 1: Gender distribution by groups, mean age and perceptions.

GROUPS	MOP+		MOP-		TOPLAM		p
	n	%	n	%	n	%	

Female	10	71,46	42,9	16	57,10		
Male	4	28,68	57,1	12	42,90		
total	14	100	14	100	28	100	
	\bar{x}	ss	\bar{x}	ss	\bar{x}	ss	p
Little irregularity index	9,99	2,63	8,87	1,50	9,42	2,17	0,179
age (years)	17,21	3,76	15,29	1,77	16,25	3,05	0,095

n: number of individuals \bar{x} : average, ss: standard deviation, p<0,05

Oral hygiene procedures were explained visually with videos and applied on the model to all patients before the treatment and in the session where the brackets were applied. It was told that they should brush their teeth at least 3 times a day, then use an interface brush, pay attention to the foods that will cause caries and avoid acidic beverages. Periodontal status of the individuals included in the study before the treatment was evaluated with the help of periodontal measurements. Oral hygiene of the individuals included in the study was checked at each session and necessary suggestions were made.

The pre-treatment routine orthodontic recordings of the individuals included in the study were performed by taking plaster model, intraoral and extraoral photographs, panoramic and lateral cephalometric radiographs and evaluations according to inclusion criteria.

In each study, clinical periodontal parameters were measured with periodontal sonde just before (T0) and after the leveling (T1) treatment. Gingival thickness measurements were performed with an

ultrasonic device (Pirop® Ultrasonic Biometer A- Scan, Echo - Son, Krancowa, Poland).

In order to evaluate the changes in the dental arch until the leveling phase was completed, each session was taken from the lower jaw and plaster models were obtained. Afterwards, digital models were created from plaster models using 3D scanning device (3Shape R700 TM Scanner, Copenhagen, Denmark).

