In our study, bracketing was performed by using MBT system brackets (Mini Master Series® 2, American Orthodontics, Sheboygan, WI, USA) with 0.022x0.028 inch slots in both groups. After bracketing and before MOP administration, patients were asked to rinse their mouth twice with chlorhexidine mouthwash, each lasting for 1 minute. In the first session, MOP application was performed with Propel® (Ossining, NY, USA) driver under local anesthesia in the areas where the dental movement was requested in accordance with the manufacturer's instructions.

Propel® is a disposable device specially designed for micro-osteoperforation. The device includes a 1.5 mm thick perforation tip. It has a depth setting of 3, 5 and 7 mm and the LED depth indicator warns when the desired depth is reached. The device was removed from its sterile packaging and, after adjusting the desired depth, was gently placed on the gum and then turned clockwise with gentle pressure. When the desired skin was reached, the LED indicator was removed by turning it counterclockwise with the indicator illuminated. Micro-osteoperforations were performed directly and atraumatically in the keratinized gum at two or three points, 3 mm between canine canine, 5 mm between canine molar, and 7 mm deep in the posterior region and 1.5 mm in diameter in the alveolar bone (2).

In each group of patients using conventional fixed orthodontic braces, leveling with 0.014 inch nickel titanium (Ni-Ti, American Orthodontics, Sheboygan, WI, USA) arc wire was started. All patients were called for monthly visits and each session was measured and a plaster model was formed until the leveling phase was completed. Ni-Ti (American Orthodontics, Sheboygan, WI, USA) wires of 0.014 inch, 0.016 inch, 0.016x0.022 inch and finally 0.019x0.025 inch were used, respectively, depending on the leveling condition. In both groups, arc wires were connected to the slots by prefabricated steel wire ligatures.

In order to evaluate the clinical efficacy of micro-osteoperforation, the following variables were evaluated in both groups at the beginning of treatment and after completion of the leveling:

- Cephalometric measurements
- Periodontal measurements
- Amount of entanglement and width of tooth arch
- Leveling time
- Pain values and patient satisfaction

Evaluation of Hard and Soft Tissue Changes

Angular and linear measurements were performed on lateral cephalometric films taken at the beginning and after treatment.

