Lateral Cephalometric Radiography

The lateral cephalometric radiographs used in the study were taken with cephalometric x-ray device (Orthopantomograph, OP300, Scanora / Instrumentarium, Tuusula, Finland) in the Department of Oral

Diagnosis and Radiology of Izmir Katip Celebi University Faculty of Dentistry. Lateral cephalometric radiographs; natural head position, teeth in centric occlusion and lips in resting position. In order to perform cephalometric analysis, 24 points were determined and 9 cephalometric planes were created. A total of 13 measurements were performed using 4 skeletal, 6 dental and 3 soft tissues using Dolphin Imaging software (version 11.8, Dolphin Imaging, Chatsworth, CA, USA).

Cephalometric Points Evaluated in the Study

The points to be used for cephalometric analysis were grouped into 3 groups as skeletal, dental and soft tissue points.

Evaluation of Periodontal Tissues

Gingival index (GI), plaque index (PI), pocket depth (PD), probing bleeding (PB) and gingival thickness (GT) were measured when immediately before placing the bracket (T0) and after completion of the leveling procedure (T1) in all patients in the study. Periodontal measurements were performed by a single researcher in order to provide standardization. Probing was performed using the Williams periodontal probe (Hu Friedy®, Chicago, IL, USA) with a diameter of 0.5 mm and a guide line at 1-2-3- 5-7-8-9-10 mm on it to facilitate measurement. The measurements were recorded in clinical forms of each patient.

The gum thickness was measured using an ultrasonic measuring device (Pirop® Ultrasonic Biometer, A- Scan, Echo - Son, Krancowa, Poland) at the midline of the tooth, perpendicular to the tooth, in the middle of the keratinized gingival width (3).

Properties of Pirop® Biometer:

1. The device measures from 0.25 to 6 mm.
2. It shows sensitivity up to 0.01 mm.
3. It has an A-scan tip at a frequency of 20 MHz (4).

4. It transmits 10 ultrasonic waves to the application area and works on the principle of giving 10 gum thickness measurements by automatically calculating the distance traveled in mm as a result of the reflection of the ultrasonic waves from the hard tissue.

5. Automatically subtracts the average value from 10 measurements and reflects the results to the 5.7- inch LCD touch screen with standard deviation.

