The Evaluation Of The Efficiency Of Micro-osteoperforation

Date :April 28, 2016

Statistical Analysis Plan (SAP)

Data were analyzed by IBM SPSS (version: 25.0, IBM Corp., Armonk, New York, USA) statistical package program. Descriptive statistical data were number of units (n), percentage (%), mean \pm standard deviation ($\bar{x} \pm$).

Correlation between the measurements (method error) was evaluated with intraclass correlation coefficient. In the assessment of the compatibility of the Model and Little perpendicularity index measurements, the intraclass correlation coefficient was specified with a 95% confidence interval.

The normal distribution of the numerical variables was evaluated by Shapiro-Wilks normality test and Q-Q graphs. Independent samples t test was used to compare the means between two independent groups of continuous measurements, and dependent sample t test was used to compare two dependent groups. Gender distribution between groups was evaluated using chi-square test.

The comparison of the groups according to time was made by means of two-way analysis of variance and generalized linear models in repeated measurements. Bonferroni test was used as multiple comparison test. The level of statistical significance was set at $p \leq 0.05$.

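### No primary outcome or decision rule is named across five unranked efficacy domains, so the error rate of the conclusion that MOP is effective is undefined

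*SAP*

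**What the plan says.** The protocol opens with a single aim: "The aim of this study was to evaluate the effectiveness of micro-osteoperforations (MOP) performed in the alignment stage". After the description of the archwires it lists what will be judged: "In order to evaluate the clinical efficacy of micro-osteoperforation, the following variables were evaluated in both groups". Five bullets follow, in no stated order of importance: cephalometric measurements, periodontal measurements, crowding and arch width, leveling time, and pain with satisfaction.

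Later sections expand these bullets. Under Lateral Cephalometric Radiography, "A total of 13 measurements were performed using 4 skeletal, 6 dental and 3 soft tissues". The periodontal section has five indices and the digital-model section five measurements, one of them the Little index. Leveling time is the number of days until the Little index falls below 1 mm. Pain and satisfaction are collected at six time points.

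The sample-size paragraph, citing a trial on mandibular anterior crowding, "showed that 24 patients had an effect width of" 1.05 and 80% power under a dependent t test. It does not say which outcome the effect size belongs to.

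On analysis over time the SAP states: "The comparison of the groups according to time was made by means of two-way analysis of variance and generalized linear models in repeated measurements". The next words are "Bonferroni test was used as multiple comparison test. The level of statistical significance was set at" 0.05. Sidedness is not given.

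**The concern.** There is one question and there are many possible answers to it. A significance level controls the error of a conclusion only when the plan says which test, or which combination of tests, delivers that conclusion. Here nothing does. Bonferroni comes straight after the repeated-measures models and is called a multiple comparison test, so it most naturally covers comparisons of times or groups within an outcome. No family of outcomes is defined to which it could otherwise apply.

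At stake is how the results may be read. With 14 patients per arm, a chance finding on any listed outcome could be presented as evidence that MOP works, and the plan contains nothing against which to check that claim.

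**Working it through.** **1. Count of outcomes.** Cephalometric 13 + periodontal 5 + model 5 + leveling time 1 + pain 1 + satisfaction 1 = 26 measurements, taking pain and satisfaction as one each. Only four have a self-evident favourable direction: Little index, leveling time, pain and satisfaction. No favourable direction is stated for the cephalometric, periodontal and arch-dimension measures.

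**2. Search for a designated outcome.** Three features point towards alignment: the alignment-stage aim, the entry rule ("Presence of more than 5 mm crowding in the lower arc according to Little irregularity index"), and the title of the sample-size source. All three fit both the Little index and leveling time. Neither is called primary, and leveling time stands fourth of five in the list.

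**3. Illustrative error rates.** These assume that MOP has no effect, that each outcome gets one two-sided t test at 0.05 with 14 per arm, and that one significant result favouring MOP would count as effectiveness. A single test then falsely favours MOP with probability 0.05/2 = 2.5%. For k independent tests the chance is 1 − 0.975^k:

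- k = 2 (Little index, leveling time): 1 − 0.975² = 4.9%
- k = 4 (adding pain and satisfaction): 1 − 0.975⁴ = 9.6%

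The documents give no correlations between outcomes, so a common correlation was assumed and null trials were simulated:

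| Outcomes | Correlation 0 | Correlation 0.9 | One test |
|---|---|---|---|
| 2 | 4.9% | 3.6% | 2.5% |
| 4 | 9.6% | 4.7% | 2.5% |

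Intermediate correlations fall between these values; for four outcomes, 0.3 gives about 8.8% and 0.6 about 7.3%. The two-outcome row probably lies nearer its lower end, because leveling time is defined by the Little index.

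If testing is one-sided at 0.05, the single-test rate is 5%, and independent tests give 1 − 0.95² = 9.8% and 1 − 0.95⁴ = 18.5%.

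**4. The plan's own figure.** For an independent t test with n per arm, the noncentrality is d√(n/2).

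- 12 per arm: 1.05 × √6 = 2.57 on 22 degrees of freedom. Power is 80.1% one-sided, which reproduces 24 patients for 80%, and 69.1% two-sided.
- 14 per arm: 1.05 × √7 = 2.78 on 26 degrees of freedom. Power is 76.2% two-sided.
- The dependent t test named in the protocol does not reproduce the figure: 24 pairs give more than 99%, and 12 pairs give 96.0% one-sided or 91.1% two-sided.

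So the stated size matches only a one-sided independent t test.

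**The case against.** The strongest objection is that no passage says one significant outcome would suffice. The protocol lists variables to be evaluated and states no rule that any one of them decides. This stands. A reader might infer that the 0.05 level is shown to fail, but the documents support only that the error rate is undefined, and that it is inflated under an any-one reading which the plan does not rule out.

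A reader might also take all 26 measurements and quote 1 − 0.95²⁶ = 73.6% as the chance of a false efficacy claim. The documents do not support that. The figure assumes independence, counts results against MOP, and counts shifts in measures with no stated direction of benefit. Some domains may be meant as safety or descriptive outcomes, although the protocol lists them all under clinical efficacy.

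The rates in the working are for single t tests, whereas the SAP plans repeated-measures analyses over several sessions. They also depend on sidedness, which the SAP leaves open. They illustrate the problem and do not estimate this plan's error rate.

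It can be argued that leveling time is plainly the main outcome. The pointers do favour alignment, but they do not choose between leveling time and the Little index, and a pointer is not a designation.

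Finally, naming an outcome now may look like a full cure. It is not. Both documents are written in the past tense, "Table 1 presents the gender, age distribution and baseline Little irregularity index data of the patients", and the digital-model section gives sixth-session model counts by arm (7 and 9). Those counts follow insertion of the final archwire, not the Little index falling below 1 mm, so they do not measure leveling time as defined. They do show that information on progress by arm was already available.

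**Conclusion.** The concern holds in a limited form. One question is put to five unranked domains with no primary outcome, hierarchy or decision rule, and the single 0.05 level is not tied to any deciding test. If any one significant outcome were read as effectiveness, the excess is modest for the two alignment outcomes (about 1.1 to 2.4 percentage points above 2.5%) and larger for the four directional outcomes (about 2.2 to 7.1 points). These sizes rest on two-sided single t tests and on assumed correlations from 0 to 0.9. The power statement is a related defect: its figure does not match the test it names. The restated two-sided power of 69% or 76% applies only if d = 1.05 belongs to the chosen outcome.

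**What to change.** In the SAP:

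- State that the effectiveness conclusion rests on one outcome, tested at 0.05 with sidedness given. It should be the outcome the investigators intended and the one to which d = 1.05 refers; name the source outcome of that effect size. Leveling time to a Little index below 1 mm is a candidate that fits the aim.
- Label every other outcome secondary or safety, report it as an estimate with a 95% confidence interval, and rest no effectiveness claim on it.
- State that Bonferroni applies to comparisons within an outcome.
- Disclose when the primary outcome was chosen relative to seeing outcome data. Naming it now does not establish prespecification.

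In the sample-size paragraph, correct the named test. If testing is two-sided and d = 1.05 applies to the chosen outcome, restate power as about 69% with 12 per arm or 76% with 14 per arm.

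No new data are needed. The cost is that isolated significant secondary results can no longer be offered as proof of efficacy, and the stated power may be lower. The gain is clear labelling and disclosure.
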